3.5.2.2 Adverse Events of Special Interest

The following events are considered to be clinically-relevant and will be summarized:

- Platelet count reduction to < 50,000/mm³ associated with major bleeding or clinically-relevant non-major bleeding
- Platelet count reduction to < 25,000/mm³, irrespective of bleeding status

3.5.2.3 Other Events of Interest

Local Cutaneous Reactions at the Injection Site (LCRIS)

Local cutaneous reactions at injection site (LCRIS) will also be summarized by the group presented in [Section 3.2.1](#) including overall using the MedDRA coding system, by system organ class and preferred term. Number and percent of patients reporting at least one LCRIS will be summarized also.

The following MedDRA preferred terms are determined by the Sponsor's Pharmacovigilance personnel to represent the local cutaneous reaction at the injection site:

- Injection site erythema
- Injection site swelling
- Injection site pruritus
- Injection site pain
- Injection site tenderness

Only events that start on the day of injection and persist for at least 2 days, i.e. event onset date on the day of injection and resolution date not on the day of injection or the day after the injection, will be included. Events with onset date on the day of injection and missing resolution date will also be included.

Percentage of injections leading to local cutaneous reactions at injection site will be summarized by the group presented in [Section 3.2.1](#) including overall using descriptive statistics.

Percentage of injections leading to local cutaneous reactions at the injection site will be calculated as follows for each patient: (A/B)*100, where A=number of injections leading to local cutaneous reactions at the injection site, and B=total number of injections.

Revised LCRIS is defined as any AE with MedDRA preferred term or verbatim that contains “INJECTION SITE”. Revised LCRIS that start on the day of injection and persist for at least 2 days, and revised LCRIS that start any time and persist for at least 2 days, will be included.

Number of total volanesorsen injections in index study and/or open-label study before the first treatment emergent revised LCRIS will be summarized.

Duration to resolution in days will be calculated as the summation of (AE end date – AE start date) + 1 for all treatment emergent LCRIS related to one injection. For LCRIS events with overlapped duration related to one injection, the earliest start date and latest end date will be used in the calculation; for unresolved LCRIS events with missing end date, the last date on study will be used in the calculation.

Discoloration

Discoloration is defined as any AE with “Injection Site Discolouration” as MedDRA preferred term. Counts and percentages of patients with any discoloration TEAE and unresolved discoloration TEAE will be summarized.

Flu-Like Reactions

Flu-like reactions (FLRs) will also be summarized by the group presented in [Section 3.2.1](#) including overall using the MedDRA coding system, by system organ class and preferred term and by preferred term only. Number and percent of patients reporting at least one FLR will be summarized also.

FLRs are defined as either (A) flu-like illness or (B) Pyrexia or feeling hot or body temperature increased, plus at least two of the following: Chills, Myalgia, and Arthralgia, starting on day of injection or the next day.

Percentage of injections leading to FLRs will be summarized by the group presented in [Section 3.2.1](#) including overall using descriptive statistics.

Percentage of the injections leading to FLRs will be calculated as follows for each patient: (A/B)*100, where A=number of injections leading to FLRs, and B=total number of injections.

Revised FLRs are defined as flu-like illness, chills, myalgia, arthralgia, pyrexia, feeling hot, body temperature increased that starts on the day of volanesorsen injection or the next day.

Bleeding Adverse Events

Treatment Emergent bleeding adverse events also will be summarized using MedDRA preferred term and system organ class. The bleeding TEAE will be defined based on the Haemorrhages (SMQ) Export from MedDRA.

The frequency of patients with any incidence of AEs and the number of events will be summarized by MedDRA preferred term (and severity) sorted by frequency for:

1. Any treatment emergent bleeding AEs for the safety set, for the subset of patients on concomitant anti-coagulant or anti-platelet medication, and for the subset of patients not on concomitant anti-coagulant or anti-platelet medication.
2. Treatment emergent bleeding AEs under contemporaneous use of concomitant anti-coagulant or anti-platelet medication for the subset of patients on concomitant anti-coagulant or anti-platelet medication.

Treatment emergent bleeding adverse events will be listed. In addition, treatment emergent bleeding adverse events will be listed by platelet count categories before and after bleeding, and anti-platelet or anti-coagulant medication.

Platelet Count Decreased/Thrombocytopenia Events

Platelet count decreased or thrombocytopenia events will be listed by preferred terms, severity, platelet count category, platelet count before (or on)/after AE, and CTCAE grade of platelet count before (or on)/after AE.

List of nadir post-baseline platelet count will be generated for patients who discontinued due to platelet count decreased or thrombocytopenia events.

Any 2 Occurrences of Platelet Count < 140,000/mm³ or Any Single Occurrence of Platelet Count <100,000/mm³

The analysis is defined in [section 3.5.4.2](#).

ALT > 3 ULN

The analysis is defined in [section 3.5.4.2](#).

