3 ANALYSIS PLAN

3.1 Statistical Design Summary

This is a multi-center open-label study of:

Group 1: ISIS 304801-CS6 (index study) roll over FCS patients

Group 2: ISIS 304801-CS16 (index study) roll over FCS patients

Group 3: FCS patients who did not participate in the ISIS 304801-CS6 or ISIS 304801-CS16 index studies.

Group 1 and Group 2 patients who complete one of the index studies and who are qualified plus Group 3 patients who are screened and qualified will be enrolled to this open-label study. The safety and efficacy of extended dosing with volanesorsen in patients with FCS will be evaluated by summary tables rather than hypothesis tests. Missing data will not be imputed.

3.1.2 *Sample Size Consideration*

No sample size calculations were performed as this is an open-label extension study.

3.1.3 *Planned Interim Analysis*

An interim analysis may be conducted after the last patient's Week 13 visit of the open-label study or after the database of the ISIS 304801-CS6 and ISIS 304801-CS16 index studies are locked and unblinded.

Planned summaries and patient data listings for disposition, demographic, efficacy and safety will be included in this interim analysis.

Additional interim analyses will be performed to support regulatory filing activities.

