3.2 General Overview of Analyses

3.2.1 *Statistical Methods*

All eCRF data, lab data transfers, as well as any outcomes derived from the data, will be provided in the patient data listings. Patient data listings will be presented for all patients enrolled into the study. Descriptive summary statistics including n, mean, median, standard deviation, standard error, interquartile range (25th percentile, 75th percentile), and range (minimum, maximum) for continuous variables, and counts and percentages for categorical variables.

Efficacy data including fasting lipid measurements, abdominal pain and QOL results will be mapped to analysis visit specified in the table below.

The intent of these visit windows is not to align with those prescribed for visit scheduling in the clinical study protocol but, rather, based on the protocol-defined target study day, to delineate mutually exclusive windows so that all efficacy assessments proximal to a particular study week can

be integrated to best represent the patient's status during that period of the study. If a patient discontinued early from the treatment period but attended applicable landmark visits at Weeks 12, 13, 25 and etc. to collect efficacy assessments, then those assessments collected at Early Termination visit and during post-treatment follow-up period should be mapped to analysis visits as well. If there are multiple assessments within a visit window, only scheduled visit will be used. If there are multiple scheduled assessments, for fasting lipid measurements and numeric QOL results, average will be used; for abdominal pain and character QOL results, the worst will be used. If the assessments are all unscheduled, the visit nearest the scheduled date will be used unless two visits are equally near, in which case the average will be used. For fasting lipid data, local lab data will not be used unless central lab assessments are not available at certain visit. When calculating the baseline and analysis endpoints, only if the data from central lab is missing, then the local lab data will be utilized.

Efficacy/PD measure	Mapped Visit (Week)	Target	Study Day Window
Fasting Lipid Assessment	Screening	-56 to -15	≤ -15
	Qual Visit	-14 to -7	-14 to <1
	1	1	1
	4	22	2 to 36
	8	50	37 to 64
	12	78	65 to 82
	13	85	83 to 106
	25	169	107 to 173
	26	176	174 to 197
	38	260	198 to 302
	50	344	303 to 351
	52	358	352 to 400
	extended treatment period		
	64	442	401 to 484
	76	526	485 to 575
	90	624	576 to 673

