3.5.1 Imputation of Missing/Partial Dates

3.5.1.1 Adverse Events

For AEs, the following imputation rules will be applied to impute start dates under conservative principles:

- If year, month and day are all missing then assign **Day 1 of Volanesorsen**.
- If month and day are missing and year is
 - The same as the year of **Day 1 of Volanesorsen** then assign the month-day of first Study Drug.
 - Earlier than the year of **Day 1 of Volanesorsen** then assign December 31.
 - After the year of **Day 1 of Volanesorsen** then assign January 1.

If only day is missing and month-year is

- The same as the month-year of **Day 1 of Volanesorsen** then assign the day of first Study Drug.
- Earlier than the month-year of **Day 1 of Volanesorsen** then assign the last day of the month.
- After the month-year of **Day 1 of Volanesorsen** then assign the first day of the month.

Imputation will be performed only for the end date only if the day or month is missing (i.e. year is present) for a resolved AE as follows:

- If month and day are missing and year is
 - The same as the year of the last dose of Study Drug then assign the month-day of the last dose of Study Drug.
 - Otherwise, assign December 31.
- If only day is missing then assign the last day of the month.

If the imputed start date is later than the imputed end date then set the imputed start date to the imputed end date.

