The incidence of patients with post-baseline platelet results falling in each of the following categories will be summarized for the safety set and the subset of patients with normal baseline ($\geq 140,000/\text{mm}^3$), and these categories will be summarized based on confirmed values as well:

- Any 2 occurrences of platelet count $< 140,000/\text{mm}^3$
- Any single occurrence of platelet count $< 100,000/\text{mm}^3$
- Any 2 occurrences of platelet count $< 140,000/\text{mm}^3$ or any single occurrence of platelet count $< 100,000/\text{mm}^3$
- Worst post-baseline value falling in: $100,000/\text{mm}^3$ to $< 140,000/\text{mm}^3$, $75,000$ to $< 100,000/\text{mm}^3$, $50,000$ to $< 75,000/\text{mm}^3$, $25,000$ to $< 50,000/\text{mm}^3$, 0 to $< 25,000/\text{mm}^3$
- Worst post-baseline platelet reduction from Baseline $\geq 30\%$ and $\geq 50\%$

The incidence of patients with post-baseline platelet results falling in each of the following categories will be summarized for the safety set and the subset of patients with normal baseline ($\geq 140,000/\text{mm}^3$):

- With ≥ 2 consecutive values of platelet count $< 140,000/\text{mm}^3$
- With platelet count $< 100,000/\text{mm}^3$ at final visit
- With ≥ 2 consecutive values of platelet count $< 140,000/\text{mm}^3$ or with platelet count $< 100,000/\text{mm}^3$ at final visit

The number of patients with any single occurrence of platelet results at any time, and during post-baseline period, falling in each of the following categories will be summarized for the safety set. These categories will be summarized based on nadir platelet values as well:

- $< 140,000/\text{mm}^3$
- $< 100,000/\text{mm}^3$
- $100,000/\text{mm}^3$ to $< 140,000/\text{mm}^3$
- $75,000$ to $< 100,000/\text{mm}^3$

- 50,000 to < 75,000/mm³
- 25,000 to < 50,000/mm³
- < 25,000/mm³

The ratio of post-baseline central lab platelet test numbers to total number of injections in open-label study will be summarized. The ratio of post-baseline central and local platelet tests numbers to total number of injections in open-label study will be also summarized.

The time to recover from confirmed platelet values <100,000/mm³ during on-study period will be calculated and summarized by all patients, and patients who complete week 52 (or week 104) with or without any dose pause/dose adjustment.

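### Unresolved injection-site reactions enter the duration-to-resolution summary with the last study date as their end, so the mean and upper tail are understated

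*SAP*

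**What the plan says.** **LCRIS.** SAP Section 3.5.2.3 states: "Duration to resolution in days will be calculated as the summation of (AE end date – AE start date) + 1", taken over all treatment-emergent LCRIS tied to one injection. Where such events overlap, the span from first start to last end is used. For events still open, "for unresolved LCRIS events with missing end date, the last date on study will be used in the calculation". The same section admits reactions that begin on the injection day and have no resolution date, so unresolved events are expected. It reports unresolved events separately for discoloration ("Counts and percentages of patients with any discoloration TEAE and unresolved discoloration TEAE will be summarized") but gives no such count for LCRIS.

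**General rules.** Section 3.5.1.1 completes an AE end date "only if the day or month is missing (i.e. year is present) for a resolved AE", so it leaves unresolved events without an end date. Section 3.1 says "Missing data will not be imputed". The LCRIS rule departs from both. The default summary for a continuous variable is in Section 3.2.1: "Descriptive summary statistics including n, mean, median, standard deviation, standard error, interquartile range" and range. Kaplan-Meier is named only for treatment continuation (Section 3.2.4).

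**Platelets.** Section 3.5.4.2 states: "The time to recover from confirmed platelet values <100,000/mm³ during on-study period will be calculated and summarized by all patients", and also by patients who complete Week 52 (or 104) with or without a dose pause or adjustment. It does not say how a patient enters the summary if the count has not recovered by the last observation.

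**The concern.** A reaction that never resolved during observation has no resolution time. It has only a lower bound, the time from onset to last contact. The rule puts that bound into the same column as observed resolution times, and the default mean and standard deviation then treat the two alike.

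The value also depends on exit route and not on the reaction alone. Under Section 2.1.5, patients who move to expanded access do not enter the 13-week post-treatment period, while those who do not move are followed for it. A persistent reaction that begins shortly before an early exit is recorded as a short one. Where reactions to one injection overlap, the latest end date governs, so a single unresolved event can set the whole value.

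At stake is the description of how long injection-site reactions last. Section 1.3 sets no formal hypothesis, so the summaries themselves are what the study delivers. The reactions of most interest here are the persistent ones, and those are the ones misdescribed.

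**Working it through.** The SAP gives no duration or unresolved count, so there is no figure of its own to reproduce.

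**1. The rule on the SAP's own study days.** Inputs: Week 52 = Day 358 (Section 1.4); Week 65 = Day 449 and Week 117 = Day 813 (sampling tables, Section 3.4.1.1). Weekly dosing from Day 1 puts the 51st injection on 1 + 7 × 50 = Day 351. Formula: end − start + 1, with the last study date as the end.

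| Same unresolved reaction, onset Day 351 | Calculation | Recorded duration |
|---|---|---|
| Leaves for expanded access at Week 52 | 358 − 351 + 1 | 8 days |
| Followed to Week 65 | 449 − 351 + 1 | 99 days |
| Extended treatment, followed to Week 117 | 813 − 351 + 1 | 463 days |

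Each value is a lower bound. Written correctly, they are at least 8, at least 99 and at least 463 days.

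**2. Effect on the summary (illustration; duration distributions assumed).** A share of reactions is long-lasting (exponential, mean 90, 180 or 365 days) and the rest last about 7 days. Onset is spread evenly over weekly injections from Day 1 to Day 351. Half of the patients exit at Day 358 and half at Day 449. Five of the twelve combinations simulated:

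| Long-lasting share, mean | Unresolved | Mean: true / SAP rule | Mean among unresolved: true / SAP rule | Median: true, SAP rule and Kaplan-Meier |
|---|---|---|---|---|
| 5%, 90 d | 1.3% | 12.8 / 12.0 | 137 / 78 | 7 |
| 10%, 180 d | 3.9% | 26.0 / 19.7 | 304 / 142 | 8 |
| 20%, 180 d | 7.3% | 43.3 / 30.8 | 325 / 153 | 8 |
| 20%, 365 d | 11.6% | 80.2 / 39.0 | 542 / 188 | 8 |
| 40%, 365 d | 22.5% | 150.1 / 68.9 | 553 / 192 | 12 |

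The two extremes of the twelve are the first and last rows. The overall mean is low by 1 − 12.0/12.8 = 6% up to 1 − 68.9/150.1 = 54%. In all twelve, the median under the SAP rule equals both the true and the Kaplan-Meier median (7 to 12 days).

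**3. Platelet recovery: what an unstated rule could do (illustration; recovery times assumed).** Recovery is exponential with mean 20, 40 or 80 days. Follow-up is 42, 84 or 91 days, matching the 6-week and 12-week platelet monitoring in Section 2.1.2 and the 13-week period in Section 2.1.5.

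| True mean | Not recovered | Mean if non-recovered are dropped | Mean if last date is taken as recovery | Kaplan-Meier median (true) |
|---|---|---|---|---|
| 20 d | 1.0–12.0% | 14.2–19.0 | 17.5–19.7 | 14 (14) |
| 40 d | 10.2–35.0% | 17.4–29.5 | 26.0–35.8 | 28 (28) |
| 80 d | 32.1–59.3% | 19.2–37.1 | 32.7–54.4 | 55–56, or not reached at 42 days (55–56) |

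These rows show why a rule is needed. They do not show what the SAP will do.

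**The case against.** **The LCRIS rule is an openly stated convention and its values are valid minimum durations.** This stands as far as it goes. AE listings keep the originally reported dates (Section 3.5.2.1), so a missing end date can still be seen there. The fault is in the summary, which labels the minimum as resolution time and shows nothing to tell the two apart.

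**A reader might infer that the rule inflates durations.** Suppose 90% of reactions last 14 days and 10% are unresolved after 182 days. The mean is 0.9 × 14 + 0.1 × 182 = 30.8 days, against a Kaplan-Meier median of 14. That comparison sets a mean against a median. The 182 days is a lower bound, so the true mean is at least 30.8 and the rule understates it. The median and both quartiles are 14 under either method. Kaplan-Meier quartiles alone would therefore add nothing in that case; the unresolved share carries the information.

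**A reader might infer that platelet recovery time is also wrong, with non-recovered patients dropped or counted as recovered.** Section 3.5.4.2 states neither. Patients who stopped treatment because of platelets are not excluded either: the summary covers all patients, and the completer split is an addition. The same section tabulates counts below 100,000/mm³ at the final visit, and Section 3.5.2.3 lists nadirs for patients who discontinued for platelet events. Non-recovery is thus partly visible elsewhere. What remains is an unstated rule.

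**Kaplan-Meier cannot simply be applied to the present measure.** This is correct. Durations of non-overlapping events are added up, and such a sum is not a time to one event. Weekly injections also give many correlated durations per patient. The fix has to deal with both.

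**Consequence is low.** This also stands: no test or sample size depends on these durations.

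**Conclusion.** The point holds for LCRIS. As written, the rule summarises a follow-up-dependent minimum as a completed resolution time, and it understates the mean and upper tail where reactions persist. The exact part is the 8, 99 or 463 days for one and the same unresolved Day 351 reaction, which assumes that the last study date falls on the scheduled day. The effect on the overall mean, 6% to 54% low, rests on assumed durations and exit days. The actual size depends on how many LCRIS are unresolved, which the SAP does not say. The median is largely unaffected.

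That the values are treated as complete is inferred from the absence of any censoring rule together with the default descriptive statistics; nothing in the SAP points the other way.

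For platelet recovery there is a gap and no demonstrated error. The importance is minor: a correction to descriptive safety tables.

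**What to change.** In Section 3.5.2.3:

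- Measure each injection's reaction as one span, from the earliest onset to the resolution of the last related event, in place of the sum of separate intervals.
- Treat the span as censored at the last study date if any related event is unresolved.
- Report Kaplan-Meier estimates that reach the upper tail, for example the share still unresolved at fixed times, and place the number and percentage unresolved beside the duration summary.
- Note that repeated injections within a patient are correlated, so any confidence interval should allow for clustering by patient. Note also that Kaplan-Meier assumes exit is unrelated to how long the reaction would have lasted.

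In Section 3.5.4.2, state that patients not recovered at their last platelet observation stay in the existing all-patients summary as censored, and show how many there are. State, or cite from the protocol, the date from which time runs and what counts as recovery for this analysis.

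The cost is a few lines of SAP text and some programming with a method that the SAP already uses for treatment continuation. No new data are needed.

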3.5.3 Vital Signs Measurements

Vital signs will include weight, BMI, body temperature, heart rate, respiratory rate, and systolic and diastolic blood pressure. Summary tables will be created to present the descriptive statistics (n, mean, standard error, standard deviation, median, 25th percentile, 75th percentile, minimum, and maximum) for vital sign values as well as the change from baseline at each study visit.

3.5.4 Laboratory Measurements

3.5.4.1 General analysis of safety laboratory data

The following is the list of lab analytes that will be collected throughout the study:

- Chemistry: Sodium, Potassium, Chloride, Bicarbonate, Total protein, Albumin, Calcium, Magnesium, Phosphorus, Glucose, Blood Urea Nitrogen (BUN), Creatinine, Uric Acid, Total bilirubin, Direct (conjugated) bilirubin, Indirect (unconjugated) bilirubin, Alanine aminotransferase (ALT), Aspartate aminotransferase (AST), and Alkaline phosphatase.
- Hematology: Red blood cells, Hemoglobin, Hematocrit, MCV, MCH, MCHC, Platelets, White blood cells (WBCs), and WBC differential in both percentage and absolute count (Neutrophils, Eosinophils, Basophils, Lymphocytes, and Monocytes)

- Coagulation: aPTT, PT, international normalized ratio (INR)
- Other assessments: hs-CRP, C5a, Bb, Sedimentation rate, De-lipidated free glycerol, Glycated Hemoglobin (HbA1c), FPG
- Urinalysis: Color, Appearance, Specific gravity, pH, Protein, Blood, Ketones, Urobilinogen, Glucose, Bilirubin, Leukocytes esterase, Nitrate, and Microscopic examination. For expanded urinalysis at certain visits, additional measurements will be performed including: Total Protein (quantitative), Microalbumin, and β 2-microglobulin. The expanded urinalysis data will be only displayed in patient data listings.

Missing WBC differential absolute counts and percentages will be derived:

If WBC differential absolute counts are missing, and percentages are available, then absolute counts will be calculated by multiplying the percentage by total WBC count. Conversely, if absolute count is available, and percentage is missing, then percentage will be calculated by dividing absolute count by the total WBC count. If neutrophils counts and percentages are missing, and segmented neutrophil and band neutrophil results are available, then neutrophils will be calculated by adding segmented neutrophils and band neutrophils.

The MDRD equation will be used to calculate Glomerular Filtration Rate (GFR) base on central lab serum creatinine ($\mu\text{mol/l}$) as:

$\text{GFR} (\text{mL/min}/1.73\text{m}^2) = 32788 \times \text{Serum Creatinine} (\mu\text{mol/l})^{-1.154} \times \text{Age}^{-0.203} \times (1.210 \text{ if Black or African American}) \times (0.742 \text{ if female}).$

All lab data will also be displayed in patient data listings based for all enrolled patients. Chemistry, hematology, coagulation, other assessments and quantitative Urinalysis (result, change from safety baseline) will be summarized using descriptive statistics (n, mean, standard error, standard deviation, median, 25th percentile, 75th percentile, minimum, and maximum) by study visit. Counts and percentages of categorical lab results, e.g. Urine protein will be provided.

